Recruitment. Our team has successfully recruited and retained at-risk adolescents and MSM and these methods will guide our project. The severity of the HIV epidemic among the Black community in Jackson has fostered an unprecedented level of willingness on the part of the community to fully support and direct youth and parents to the proposed study (see letters of support). As suggested in our focus groups in Jackson, the project will be called "Family Table Talk: Building Healthy Relationships for Straight and Gay Teens," or something similar. We will enroll adolescents and parents/caregivers who indicate interest in healthy adolescent relationships and acceptance of straight and gay adolescents. The project will not require adolescents to reveal their sexual behavior or attitudes. The project will use two experienced community recruiters with close ties to adolescent and LGBT relevant CBOs (My Brother's Keeper, the Teen Program of Mississippi First, GSA of Jackson, see Resources), agencies / clinics (adolescent health, HIV and STI clinics, and schools (via referral from school health and guidance counselors). Recruiters will publicize the project to youth at agency functions and with flyers/social media announcements. The agencies and schools will also direct potentially at-risk youth to the project. We will also utilize targeted advertisements posted on online social media platforms (e.g. SnapChat, Instagram, and/or Twitter) to recruit nHBAM. Referrals and advertisements will provide the contact information of the study project director, who will promptly initiate contact and seek parent consent if the youth is interested. Our Advisory Board, peer ambassadors and currently enrolled participants will also assist in recruitment. Currently enrolled participants will be incentivized to recruit up to five new participants and will receive an additional \$10 for each referral that is enrolled in the study. The Jackson urban area has a population of 574,998; 26% are under the age of 18, 48% are male, half are adolescents, and 5% will identify as non-heterosexual. (64) Based on these estimates, we will be recruiting a total of 97 non-heterosexual Black adolescent males (nHBAM) for all phases of the project from a pool of at least 1,794 non-heterosexual adolescent males in this urban area. In other projects, [name] has enrolled 1,923 at-risk adolescents with parental consent by similar methods in 5 NIH-

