Randomization: Immediately after completing baseline assessment, small block randomization (via REDCap) will create groups balanced on age and on the proportion who identify as nHBAM. We estimate that 90% of those enrolled will be nHBAM. 72 participants will provide sufficient power for the analyses (see Data Analysis). Recruitment will continue until 72 nHBAM are enrolled.

Format: Immediately after randomization, participants (adolescents and parents/caregivers) in the active (MySTYLE) condition will receive two secure, HIPAA compliant texts or emails to their mobile phones or preferred indicated device each week for eight weeks and each text/email will contain a link to new media content (overall, at least 120 minutes of multimedia time is planned, not including participant replays, which is comparable to our interactive DVD and to an online RCT conducted by Mustanski and colleagues). (9) The weekly content, as well other content and interactive materials, will be available on their condition's secure website. All nHBAM and enrolled parents/caregivers will each have their own links with separate, but parallel, content (see Figure below in Intervention Conditions). Those participants assigned to the waitlist will be eligible to participate in MySTYLE after they have completed their 2- and 4-month assessments. They then will receive two secure, HIPAA compliant texts or emails to their mobile phones or preferred indicated device each week for eight weeks and complete further assessments at 6 and 8 months. If those enrolled in the waitlist choose to participate in MySTYLE, they will have the opportunity to include their parent mid-intervention. During the 4 months that the participant is on the waitlist, study staff will not engage with the parent.

Intervention fidelity and usage: The twice-weekly video/graphic content will be embedded in the participant's unique REDCap link, providing data on the number of videos viewed by each participant. The participant will not proceed to the next web page (containing options for their weekly practice, etc.) until the video has fully played, but it may be paused and resumed later. The videos/graphics will be posted on the website for repeat viewing. Analytics will be collected on the number of minutes enrolled nHBAM spend viewing project materials, the content accessed, and the number of times any one video was re-played.

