Nonheterosexual orientation: Because youth are enrolling in a project to promote Straight – Gay Acceptance, we anticipate that nearly all will be nonheterosexual, that is they will identify with at least one of the following categories: a) have had at least one non-coercive intimate sexual experience (e.g., prolonged kissing, oral sex, anal sex) with a male, b) expect to someday have a male sex partner, c) sexually aroused by and attracted to males, or d) selfidentify as gay, bisexual, gender-queer, or other term that is not heterosexual. In addition to determining feasibility and acceptability of MySTYLE, the purpose of the small RCT conducted is to determine effect size differences in knowledge, attitudes, and behaviors. Given the reality of effect decay and the constraints of the R34, we will use only two follow-up assessments at 2 and 4 months after baseline. Participants assigned to the waitlist control condition will also complete assessments at 6 and 8 months. Scale score outcomes include relevant knowledge (e.g. HIV/ STIs), attitudes (e.g. internalized stigma, condom attitudes) and behavior (e.g. prevention self-efficacy, parental monitoring of teens' activities and companions, and practice exercises) (see Appendix 2). Scales will be adapted for nHBAM from those used in STYLE or by our investigators. Table 1 summarizes our central measures, as a function of the Social Personal Framework, and others may be added as needed based on our formative work. **Behavioral outcomes** are: (1) the number of condomless sex acts during the follow-up period. (2) the rate of onset of sexual activity and (3) the acceptance of an HIV test. Sexual behaviors. HIV testing history and STI history will be assessed in a computer-assisted self-interview designed specifically for use with adolescents and using branching logic so that they only answer items that are relevant. (76-78) As a dependent variable, adolescents will be offered a free point-ofcare (POC) HIV test at 4. Also, self-report of prior HIV and STI testing will be assessed. Those who are not yet sexually active may decide against HIV testing and we will analyze the differences in testing rates separately based on self-report of sexual activity. Our outcome is testing, rather than the HIV or STI results because rates of infection will likely be low at this age, although the study will provide data on this issue in our high-prevalence city of Jackson, MS. Intervention content acceptability: At 2 or 6 months, depending on assigned condition, adolescents will complete the CSQ (see Year 2) to assess relevance and utility of the content and to aid in refinement of the intervention, if needed, prior to a subsequent, larger RCT.

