Power. Although pilot studies are not typically powered for significance testing, (103) the RCT of 72 will nonetheless provide a "signal" of impact regarding major outcomes – e.g. CSAs, HIV testing, parenting practices. We conservatively assume that retention of 72 participants over 4 months is 85%, based on previous trials. Power analyses for knowledge, attitudes, and family practices were run with Optimal Design 3.01⁽¹¹⁷⁾ and assumed 3 assessments nested within cases. The HLM analyses with alpha of 0.05 and power 0.80 will be able to detect an effect size .41 SD for change in the scale score outcomes. If the alpha is 0.1 (as is appropriate in exploratory research), then power is 0.80 to detect an effect size of .36 SD, so this study should detect meaningful "signals" of impact. Power estimates for the behavioral counts were estimated using Mplus simulation utility using estimates from [name] previous prevention trials with adolescents. As expected, the study will be powered to detect medium to large effect sizes (rate-ratios/odds ratios ranging from 2.67 to 6.05). These combined data (scale scores, behavior outcomes, acceptability) will be used to revise intervention content and procedures, as indicated, and to prepare for a larger, definitive efficacy trial.

Protection of Human Subjects and Safety Monitoring Plan

Please note: In the Human Subjects section, we use the term **parent** to refer to the legal guardian of the adolescent and **caregiver** to refer to any family member or trusted, involved adult. Parent engagement in the RCT phase is desirable; however, caregiver engagement is also acceptable to meet the needs of the intended intervention (MySTYLE).

Human Subjects Involvement, Characteristics and Design

The program will be described in recruitment and advertisements as building healthy adolescent relationships and acceptance of straight and gay adolescents. Parents will be approached for consent after the teens have indicated an interest in the project, which will not reveal the adolescent's sexual orientation or behavior, only an interest in participating.

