Formative phase and pilot trial parent or caregiver enrollment: Parents will be contacted by phone and written informed consent for a son's participation obtained in person. If the parent (legal guardian) agrees to their son's participation in the project but does not want to participate, the parent and adolescent can nominate "someone important in the life of the adolescent such as other family, teacher, religious leader, or social worker" who will be contacted for enrollment. Caregivers will not be enrolled in lieu of a parent unless the parent agrees. This option of involving a caregiver, rather than a parent, worked well in Project STYLE, and involving a non-parental adult was recently recommended as an intervention option for non-heterosexual adolescents.⁽⁶⁹⁾ Even if a parent/caregiver never participates in the intervention, MySTYLE, may improve the family climate by focusing on healthy family communication, similar to other studies finding an impact without all family members attending sessions.⁽⁷⁰⁾

RCT enrollment: For the RCT phase a waiver of parental consent will be utilized for those under 18 and youth aged 18 or older will be able to provide their own consent. A waiver of parental consent for those under 18 produces a sample that is more diverse in terms of the extent to which nHBAM have disclosed their sexual attitudes to others, their degree of perceived stigma and discrimination, and their perceived support from, and engagement with, parents.

The RCT allows nHBAM into the program before parent/caregiver involvement with a waiver of parental consent for those under 18 and then prepares nHBAM to safely involve their parent, if possible. nHBAM aged 18 or older will be able to provide their own consent, although we will ask for permission to enroll parents/caregivers, if possible and safe for the youth. The project will be described as a general sexual health intervention for adolescent males; it will not disclose the adolescent's private behaviors or attitudes and will not require adolescents to disclose any personal information. Parent/Caregiver involvement may begin at study entry or at mid-intervention, after the nHBAM has had more time to consider it. After the adolescent provides permission to contact their parent/caregiver for enrollment, we will follow the parent/caregiver consent procedures described above in the formative and pilot trial phases. Parents/caregivers will be assigned to the same condition as their adolescents.

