One final protection involves the disclosure by study participants ages 14 and under that they have had sex with partners who are at least 24 months older than the minor and 15 to 17 years old that they have had sex with partners who are at least 36 months older than the minor. Mississippi's law requires immediate reporting of these cases to the Mississippi Department of Human Services (MDHS). [name] has created a protocol that will be applied to this circumstance, should it arise. It is important to note that our assessment instruments do not ask study participants about the age of their sex partners. However, we do clearly recognize the possibility that young male study participants may volunteer such information to the study staff during interviews or in the course of the assessments. In brief, clinic policy requires that the person to whom the information was disclosed should immediately report to MDHS Child Protective Services the incident by calling the statewide toll free [contact]). The report is then screened by a MDHS supervisor to decide whether it should be investigated. Thus, if a minor in our study discloses having sex with an adult (at least 36 months older than the minor) this mandatory reporting protocol is activated. Any male study participant ages 17 and under will be told that the health department is obligated to report to the state any instance of sex with older men (if at least 24 months older than the minor for those 14 and under and 36 months older than the minor for youth ages 15-17). [name] employs three full-time case managers who are trained counselors and will be on-hand to handle instances where a 15-17 year old discloses sex with an adult to a member of the research staff. The case managers provide additional evaluation to assure the welfare of the minor.

Adverse Reactions from Parent/caregivers. The project will be described as an intervention developing as building healthy adolescent relationships and acceptance of straight and gay adolescents; it will not disclose the adolescent's private behaviors or attitudes; and will not

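### The plan gives three conflicting descriptions of the project to parents, and says approaching them will not reveal orientation although its own reasoning makes participation informative about it

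*Combined protocol and SAP*

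**What the plan says.** Three descriptions of the project are in force.

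- **Straight and gay.** Human Subjects Involvement, Characteristics and Design says that recruitment and advertisements present the programme as building "acceptance of straight and gay adolescents". Adverse Reactions from Parent/caregivers uses the same phrase as part of the protection against harm at home. Neither place is limited to one phase.
- **Neutral.** Parent or caregiver enrollment (RCT Phase) and RCT enrollment (Protection of Human Subjects) both state: "The project will be described as a general sexual health intervention for adolescent males".
- **All backgrounds.** Recruitment and Informed Consent describes a programme of health and acceptance for young Black men whatever their sexual, economic or family background.

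On disclosure, the Human Subjects section says that approaching parents will not reveal the youth's "sexual orientation or behavior, only an interest in participating". Recruitment and Informed Consent makes the same claim in similar words.

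On who will enrol, Measures for the Randomized Trial reasons that, because youths are joining a project on straight-gay acceptance, "we anticipate that nearly all will be nonheterosexual". The Randomization section adds: "We estimate that 90% of those enrolled will be nHBAM".

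**The concern.** The investigators infer orientation from the fact that a youth joins a project of this kind. A parent or caregiver who hears the same description can make the same inference. An unqualified statement that the approach reveals only interest is therefore at odds with the plan's own reasoning.

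Staff also cannot tell from the plan which description to give an RCT parent. RCT enrollment refers back to the consent procedures of the formative and pilot phases, and the protection section for adverse parental reactions uses the straight-and-gay wording rather than the neutral one.

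What is at stake is a risk the plan itself lists. Potential Risks names adverse parental reactions, and the section on those reactions includes threats, abuse and a youth being asked to move out. The Emotional Distress section presents the programme description as one way of reducing unintended disclosure. A youth deciding whether to allow contact with a parent may rely on the assurance as written.

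**Working it through.** **Step 1. Compare the descriptions.** The neutral wording is specific to the RCT. The straight-and-gay wording stands in two human-subjects sections without a phase limit, and the Measures section applies that framing to the RCT itself. Recruitment and Informed Consent covers all phases and names the randomized trial. The three descriptions therefore overlap on the RCT and have to be reconciled.

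**Step 2. Reproduce the plan's base rate.** The Recruitment section starts from 574,998 residents and applies four proportions in turn: 0.26 (minors), 0.48 (males), 0.5 (adolescents) and 0.05 (non-heterosexual). For the last two, its words are "half are adolescents, and 5% will identify as non-heterosexual".

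- Adolescent males: 574,998 × 0.26 × 0.48 × 0.5 = 35,879.9
- Non-heterosexual among them: 35,879.9 × 0.05 = 1,794.0

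The stated pool is at least 1,794, so the figure reproduces. The 5% is the plan's own working rate for local adolescent males.

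**Step 3. Set it against the expected enrolment mix.**

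| Group | Share non-heterosexual | Source |
|---|---|---|
| Local adolescent males | 5% | Recruitment |
| RCT enrollees, expected | 90% | Randomization |
| Preparatory focus groups | 16/17 = 94% | Specific Aims |

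The exact 95% confidence interval for 16/17 is 71% to 99.9%. Participation would carry no information only if the two shares were equal, and 71% is still far above 5%.

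**Step 4. Check the definitions.** The 5% is by self-identification, as is the 16/17. The Measures section uses a wider four-part definition, under which the base rate could exceed 5%. The documents give no figure for that. At assumed base rates of 10%, 20% or 30%, the 90% remains well above, so the direction does not depend on the definition.

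**Step 5. Ask what causes the difference.** The Measures section attributes the mix to the nature of the project. Overview and Premise attributes it to venues that serve this group and to recruiters who know the LGBT community. Nothing in the plan separates the two. The 5% and 90% therefore show that taking part is informative; they do not show how much of that is due to the description.

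**The case against.** The strongest reply is that the description is one safeguard among several. In the RCT, parents are contacted only with the youth's permission, reluctant youths are not pressed and those under 18 continue under the consent waiver, and a Self-Safety Evaluation guides decisions about disclosure. The section on adverse parental reactions promises only that the project will not itself disclose, and then concedes that some parents may discover their son's orientation. All of this stands. It means that the description cannot be called the main protection, and that the fault is narrow: the unqualified assurance in two sections, and the unreconciled descriptions. The safeguards do not cure either.

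Three stronger readings are tempting and should not be adopted.

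- **An odds multiplier.** A reader might compute (0.90/0.10)/(0.05/0.95) = 171 and credit it to the straight-and-gay name. The arithmetic is right, but the attribution is not supported, for the reason in Step 5. The value is also unstable: assumed base rates of 10%, 20% and 30% give 81, 36 and 21. A parent has their own prior view of their son and is not told the 90%, and the share among youths who permit contact is not given.
- **Unequal withdrawals.** A reader might infer that withdrawals after disclosure would fall mainly in the active arm, because staff do not engage waitlist parents for four months. That is plausible, but the documents give no rate, and a household member can learn of participation in either arm.
- **Exposure through messages and mailings.** A reader might assume that text or e-mail headers, gift cards and the mailed test kit carry the project name. No section says so.

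**Conclusion.** The concern holds in a limited form. The plan gives conflicting descriptions of the project to parents that all bear on the RCT, and in two sections it gives an assurance about orientation that its own Measures and Randomization sections contradict in probability, though not with certainty. On the plan's figures, 5% of local adolescent males and 90% of expected enrollees are non-heterosexual. That contrast belongs to participation as a whole, including the effect of where and by whom youths are recruited. The conclusion rests on taking both percentages as the plan states them and on reading the human-subjects sections as applying to the RCT, since they set no phase limit. It needs no assumption about how often disclosure would occur, and it makes no claim about the trial's estimates.

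**What to change.** 1. Bring Human Subjects Involvement, Characteristics and Design, Recruitment and Informed Consent, and Adverse Reactions from Parent/caregivers into line with the two RCT enrollment sections, so that first contact with an RCT parent or caregiver (script and study title) uses the neutral description.
2. Replace the unqualified assurance with a statement that staff will not disclose a youth's orientation, but that taking part may allow others to infer it.
3. Tell youths this before they give permission to contact a parent or caregiver.

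The cost is an IRB amendment with revised scripts and wording. The design, youth recruitment and analysis are unchanged. Two limits remain. Parents and caregivers are participants too, so their own consent must still describe the intervention content accurately, whatever the title says. And public advertisements aimed at youths under the existing name can still be seen by family members, so the change reduces this route of disclosure without closing it.
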